8.3.6 Patient-reported Outcomes and Questionnaires

The patient-reported outcomes and questionnaires will be obtained at every study visit, as well as every 3 months for up to 1 year following the completion of the last study visit, unless otherwise specified. Completion of the self-reported outcome and questionnaires may be completed digitally and/or by paper format.

8.3.6.1 Short-Form Health Survey (SF36v2)

The SF36v2 is widely used throughout the world as an instrument to measure general health-related QOL in eight domains and yields physical and mental component summary scores. It is a generic measure, as opposed to one that targets a specific age, disease, or treatment group ([122](#)). SF36 has already been used among survivors of COVID-19 ([60](#)) and is a recommended outcome during the rehabilitation period ([123](#)) after COVID-19. This instrument is validated in Spanish.

8.3.6.2 EuroQoL 5-Dimension 5-Level (EQ-5D-5L)

The EQ-5D-5L is a health-related QOL questionnaire consisting of 5 questions and 1 visual analog scale. It has been validated in patients with chronic obstructive pulmonary disease and found to be responsive to changes following pulmonary rehabilitation ([124](#)). It is a recommended COVID-19 core outcome measure of QOL by the American Physical Therapy Association (APTA) ([119](#)). This instrument is available in Spanish.

8.3.6.3 Patient-Reported Outcomes Measurement Information System (PROMIS)

PROMIS is a self-reported set of measures to characterize health related quality of life for the general population and those with chronic conditions. Specifically, the PROMIS-57 is a profile instrument consisting of 57 questions, spanning 7 domains including physical function, depression, anxiety, pain interference, fatigue, sleep disturbance and ability to participate in social roles/activities. Other PROMIS scales such as dyspnea severity and functional limitations may also be used. These instruments are validated in Spanish.

8.3.6.4 Quality of Life in Neurological Disorders (Neuro-QoL)

Neuro-QOL is a set of self-report measures to assess health-related quality of life in those with neurological disorders. Specifically, the Neuro-QOL Cognitive Function v2.0 is a single short-form consisting of 8 questions that assesses adult cognitive function in 2 domains related to executive function and general concerns. This instrument is validated in Spanish.

8.3.6.5 Fatigue Severity Scale (FSS)

The FSS is used to monitor change in fatigue in response to therapeutic interventions. This scale is composed of nine items with a seven-point response format. A response of one indicates strong disagreement and a response of seven indicate strong agreement with statements regarding how fatigue affects physical and social functioning. Clinical improvement in fatigue is associated with reductions in scores on the FSS. The FSS is also a practical measure due to its brevity and ease of administration and scoring ([125](#)). It has been used to detect changes in fatigue severity with exercise intervention among patients with advance lung disease ([64](#)). This instrument is available in Spanish.

8.3.6.6 Visual Analogue Scale for Chronic Fatigue Syndrome Symptoms (VAS-CFS Symptoms)

The VAS-CFS consists of 12 items related to physical fatigue, mental fatigue or mental fog, muscle aches, muscle weakness, headache, joint aches, lightheadedness, “flu-like” symptoms, sore throat, gastrointestinal discomfort, shortness of breath, and environmental sensitivity. This questionnaire takes about 2 minutes to administer. This instrument has not been validated in Spanish.

The VAS-CFS will be used to capture changes associated with post-exertional malaise, and will be repeated up to seven times around the CPET to include prior to the CPET, ~15 minutes after the CPET, ~60 minutes after the CPET, ~4 hours after the CPET, ~24 hours after the CPET, ~48 hours after the CPET, and ~72 hours after the CPET. The VAS-CFS will only be obtained at every study visit, and not during the 1-year follow-up.

The VAS-CFS may be accompanied by a brief qualitative interview to capture unique experiences of participants before and after the CPET. An interviewer guide will structure and direct the interviews so that participants are prompted to explain their experiences in detail, but interviewers will have discretion to modify as appropriate. The interviewing guide will include the following basic questions: 1) I am interested in how you feel right now, physically, cognitively, and emotionally; 2) What symptoms are bothering you the most right now?; 3) Is how you feel right now typical for how you feel on an average day (since you were infected with COVID-19?); 4) Is how you feel right now different from how you used to feel after exertion before you were infected with COVID-19?; 5) Is there anything else you would like to add about how you are feeling right now?. Data collected during qualitative interviews will consist of audio recordings. Persons who decline to be audio-taped will not be included in the qualitative portion of the study.

An in-depth qualitative analysis process, thematic analysis, will be used to systematically code and categorize the textual data. Investigators will read over the transcripts several times to allow immersion into the data, and then construct a preliminary categorical structure or “coding scheme.” They will then independently “code” all the transcripts (i.e. the textual data), which involves identifying salient categories, collating those categories into overarching themes, and assigning names to the themes. Codes will be compared to identify disagreements and meetings will be conducted to discuss coding differences at-length and reach consensus. A qualitative software package (such as MAXQDA) will be used to highlight text within the transcripts and create categories and sub-categories electronically.

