To minimize risk and maximize safety, participants will be evaluated by NIH cardiology, perform medical history and physical examination, ECG, Doppler cardiac echocardiography, and pulmonary function tests with DLCO, to exclude those with contraindications to exercise prior to the CPET. During the CPET, participants will be monitored by continuous 12-lead ECG. Prior to beginning the test, participants will be informed of the signs and symptoms of heart disease and questioned frequently during the test regarding their presence. As recommended by the American Heart Association and the American College of Sports Medicine (ACSM), exercise will be overseen by personnel appropriately trained in clinical exercise testing ([49](#)). In addition, a licensed independent practitioner (LIP) will be present during all exercise tests. The investigators and clinical exercise training and testing staff in our laboratory are highly experienced in cardiopulmonary exercise testing, even in high-risk patients such as those with pulmonary artery hypertension and interstitial lung disease. As PEM may develop even among those reporting no PEM on enrollment, the presence of significant symptoms consistent with PEM may be captured during the qualitative interviews. These interviews were specifically developed to detect the presence of PEM and are performed by LIPs and/or persons with experience and skill conducting interviews for identifying the presence of PEM. The impact of exercise on post COVID-19 condition and PEM is still unresolved, therefore the clinical team will monitor for possible development of PEM symptoms throughout the study and manage participants accordingly.

Risk of injury also includes those related to falling on a moving treadmill belt, such as abrasions, contusions, cuts, sprains, and fractures. The likelihood that any of these injuries would occur is small and preventive measures will be enforced to ensure that the risks remain at a minimum.

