- All participants will perform the CPET with 12-lead ECG at the CC that is monitored by credentialed RMD staff members experienced with clinical exercise testing
- Gradual exercise progression with supervision by RMD staff members specifically credentialed for the supervision of aerobic exercise in clinical populations
- Thrice weekly check-ins to include monitoring of vital signs and symptoms before and after exercise during the 10 week AET intervention

Considerable overlap has been observed between the constellation of persisting symptoms in the post COVID-19 condition and ME/CFS (53). Featured among them is PEM, which was self-reported in 59% of surveyed participants reporting sequelae post COVID-19 (30). The distinguishing nature of PEM is the wide variety of worsening symptoms that may occur among individuals (from physical/mental fatigue to cold-like symptoms) and the onset or duration of symptoms (from hour to days) (54). Triggers of PEM not only include physical activity, but also mental effort and emotional stressors (54). It was recently observed that individuals identified as having PEM and post-acute sequelae of SARS-CoV2 (PASC) showed a multitude of abnormalities following a CPET, compared to a control group of individuals that had no lingering symptoms post COVID-19 (48). These abnormalities included compositional changes in skeletal muscle fibers, metabolic dysfunction, and muscle tissue damage in samples taken the day after the CPET (48). However, repeated muscle biopsies may have affected some of these findings, as the control group also showed these changes and interactions for group and time were not significant. Further, the PASC group averaged 17.9 months since initial infection, which was almost 4 times longer than the control group at 4.7 months. This extended duration of living with PASC may also account for some of the observed differences.

Specifically for PASC patients experiencing PEM, exercise recommendations “...*should follow a slow, progressive approach and be regularly evaluated in regard to symptom severity and the health status of patients*” (55). The following considerations are in place to minimize risk for patients that have or develop PEM during the study:

- Screening prior to enrollment to exclude potential participants that are identified as having PEM
- Perform assessment of PEM during H&Ps, and as needed throughout the study, by NIH medical staff for management of participants.

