- Perform qualitative interviews before, during and after the CPET to monitor the development of significant symptoms consistent with PEM. Interviews are performed by LIPs and/or persons with experience and skill conducting interviews for identifying the presence of PEM.

- Gradual exercise progression with supervision by RMD staff members specifically credentialed for the supervision of aerobic exercise in clinical populations
- Assess and monitor symptoms and tolerance of previous exercise sessions by RMD staff members to adjust exercise sessions as necessary.

In general, health risks during exercise are very small. These risks are considered to be even smaller when maximal exercise evaluations are performed under supervised and safe clinical conditions, and additional medical tests and examinations related to defining the seriousness of the patients' conditions are performed. Improvement in cardiorespiratory fitness enables individuals to accomplish a given amount of activity or work at a lower percentage of their peak capacity and with less fatigue. Moreover, improvement of exercise tolerance generally increases quality of life by permitting individuals to engage more easily in daily physical activities. Specifically as it pertains to COVID-19, "...there is a strong rationale for incorporation of exercise prescription in management of Long COVID based on cardiac deconditioning as a major contributor to symptom burden and the well-described physiologic responses (and benefits) of exercise on the cardiovascular system"([56](#)). Early reviews of the available literature on exercise training post-COVID suggest improved physical functioning and quality of life among non-hospitalized ([55](#)) and hospitalized ([57](#)) individuals. It is anticipated that the potential benefits of participating in an aerobic exercise conditioning program outweighs the minimal risks associated with exercise in patients recovering from COVID-19. Thus, this protocol involves greater than minimal risk to study participants, with the prospect of direct benefit to individual participants.

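### The PEM interviews around the CPET are presented as a planned safeguard, but section 8.3.6.6 makes them discretionary and leaves out participants who decline audio recording

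*Combined protocol and SAP*

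**What the plan says.** The risk sections treat the interviews as a safety measure. Section 2.3.1.8 recognises that PEM may appear in people who reported none at enrolment, says that "the presence of significant symptoms consistent with PEM may be captured during the qualitative interviews", and adds: "These interviews were specifically developed to detect the presence of PEM". Section 2.3.3 opens a list with "The following considerations are in place to minimize risk for patients that have or develop PEM during the study", and one item on that list, stated without condition, is: "Perform qualitative interviews before, during and after the CPET to monitor the development of significant symptoms consistent with PEM". The schedule of activities (1.3) marks the interviews, in one row with the VAS-CFS, at every study visit; the optional assessments have a separate row.

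Section 8.3.6.6 describes the same interviews as a research component: "The VAS-CFS may be accompanied by a brief qualitative interview to capture unique experiences of participants before and after the CPET". Interviewers follow a guide that they may modify. "Data collected during qualitative interviews will consist of audio recordings", and the section then says: "Persons who decline to be audio-taped will not be included in the qualitative portion of the study". The next paragraph sets out thematic analysis of the transcripts. No interview without recording is described.

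**The concern.** A measure cited in the risk-benefit assessment is made optional by the section that governs its conduct, and is tied to a research permission unrelated to the participant's safety. Section 2.3.1.8 says it is not known whether the CPET may cause lasting muscle damage, or in whom, so detection of PEM after the test is one of the matters on which the risk argument leans.

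Three things are at stake. A participant who declines taping may undergo the same symptom-limited test with one named PEM check fewer. Detection of PEM may then differ by willingness to be recorded, which makes any account of PEM in the trial less complete in a selective way. And staff cannot tell whether a skipped interview is acceptable: section 8.3 accepts omitted assessments as expected unless they are needed to judge the safety of a procedure, and the protocol gives the interview both roles.

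**Working it through.** The plan states no figure on this point, so the check is mainly a comparison of the sections, followed by one count.

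**1. The same interviews, section by section.**

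| Feature | Sections 2.3.1.8, 2.3.3 and 1.3 | Section 8.3.6.6 |
|---|---|---|
| Purpose | Detecting and monitoring PEM | Capturing individual experience around the test |
| Status | Unconditional item in 2.3.3; marked at every study visit in 1.3; permissive about what they capture in 2.3.1.8 | "The VAS-CFS may be accompanied by a brief qualitative interview" |
| Timing | Before, during and after the CPET (2.3.3); before and up to 72 hours after (1.3) | Before and after |
| Who is covered | No restriction stated | Excludes those who decline taping |
| Unrecorded version | Not addressed | None described |

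The rows on status, timing and coverage cannot all be followed as written.

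**2. What remains for someone who declines taping.**

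- VAS-CFS (8.3.6.6): as many as seven readings, the last about 72 hours after the test. No action level is stated, and the section says it lacks validation in Spanish, although Spanish speakers are eligible (5.1).
- PEM assessment by medical staff at the history and physical, and when needed (2.3.3, 8.2.1).
- Staff checks of how the previous training session was tolerated (2.3.1.15, 2.3.3).
- Adverse-event inquiry at each study visit (8.4.4).
- A general duty on the clinical team to monitor for PEM and manage participants (2.3.1.8).

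The enrolment screen (5.1) has also removed people with PEM on the DSQ-PEM.

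**3. Do these cover the same window?** Section 2.2 cites symptoms typically worsening 12 to 48 hours after activity. Section 2.3.1.8 places the baseline history and physical before the CPET, and later PEM assessment as needed requires a prompt. The session checks ask about the previous training session: there is none before the first session, control participants have no training between Visits 1 and 2, and AET+ participants have none after Visit 2. Of the scheduled tools, the VAS-CFS is therefore the one that clearly spans 24 to 72 hours without a recording.

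**4. How an answer reaches the clinical team.** Sections 8.3.6.6 and 10.8.1 take interview data from audio to transcript to coding. By contrast, the BDI-II has a notification step (8.3.6.7) and the IES-R a threshold with follow-up (8.3.6.8). Neither the interview nor the VAS-CFS has an equivalent.

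**5. Number of tests.** The CPET is done at every study visit (8.3.5.3): two visits for AET+, three for CON. With 38 completers per arm (9.2):

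38 × 2 + 38 × 3 = 76 + 114 = 190.

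This is a maximum for the 76 completers, because 9.2 counts a participant as complete once the second visit is done. CPETs in randomised participants who do not complete are not in this count. The number without an interview is 190 times the refusal rate, plus any interviews skipped at discretion. The documents give neither quantity.

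**The case against.** The strongest reply is that the protocol does not rest on the interviews. Section 2.3.1.8 is itself permissive about what they may capture, and it goes on to give monitoring to the clinical team. The other safeguards in step 2 need no recording, and section 10.6 adds regular staff meetings on each participant while the intervention is under way. This stands. A reader might infer that a decliner is left with the self-rated VAS-CFS alone; the documents do not support that.

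Next, being left out of the qualitative portion may mean only exclusion from the coded dataset, since thematic analysis is the next topic. That reading is possible. It would be wrong to say that the text certainly denies PEM questioning to decliners. But the only interview procedure described is the recorded one, and the documents nowhere say that an unrecorded one takes its place. The consent pages are not in the material reviewed, so what consent says about taping cannot be judged.

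Third, a reader might infer that a PEM-consistent answer has no route to the clinicians. That goes too far. Interviewers are licensed independent practitioners or people skilled in identifying PEM, and all adverse events on study must be documented (8.4.4). What stands is that the route from interview answer to clinical team is not stated, whereas neighbouring instruments have one.

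**Conclusion.** The inconsistency is in the text. The risk sections and the schedule present the interviews as a planned PEM measure; section 8.3.6.6 makes them discretionary, narrows their timing relative to 2.3.3 and leaves out decliners. Part of the PEM monitoring around the CPET therefore depends on consent to recording. The loss is partial, and it matters most in the days after the test, where the other scheduled checks are thinnest.

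Its size cannot be estimated. The documents support only the ceiling of 190 CPETs among 76 completers, which assumes that every CON completer attends Visit 3. It is tempting to multiply by a guessed refusal rate: 10% to 30% would give 19 to 57 tests. Nothing in the documents supports that range, so the result only restates the guess.

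The conclusion assumes that section 8.3.6.6 is the operating text and that no unrecorded PEM interview is specified elsewhere. The 6MWT endpoint and its analysis are not affected. The point should still be corrected, because a safeguard cited in the risk-benefit case should not turn on permission to record.

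**What to change.** Reconcile sections 1.3, 2.3.1.8, 2.3.3 and 8.3.6.6, so that they agree on whether the interview is a safety procedure or a research component, on its timing (including whether any part takes place during the CPET) and on whom it covers.

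In 8.3.6.6, separate the PEM questions from the research recording. The existing interview questions would be asked of every participant at each CPET, with written notes where taping is declined; only audio recording and thematic analysis would stay optional. State how PEM-consistent answers reach the clinical team that 2.3.1.8 makes responsible for monitoring. What follows from an answer remains with that team. The text should also make clear how the omission rule in 8.3 applies to this interview.

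The cost is protocol and consent wording, since the question guide and skilled interviewers are already planned. The downside is a few minutes of unrecorded interview for each decliner, whose answers cannot be coded verbatim.

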8.3.6.7 Beck’s Depression Index-2 (BDI-II)

A self-report tool that measures the severity of depression and its interaction with other mood states. The BDI-II is a frequently used tool in clinical studies of depression and mood and in clinical evaluation. It has also been used to detect changes in depressive symptoms among patients with chronic obstructive pulmonary disease following pulmonary rehabilitation ([126](#)). This instrument is validated in Spanish.

Should a participant indicate severe depressive symptoms and/or suicidal ideation, the study coordinator or research staff member will remain with the participant and the PI will be notified. The PI or RMD medical staff will assess any issues that arise such as suicidal ideation. Other emergent psychiatric evaluation and treatment will be performed under the guidance of the

NIMH Psychiatry Consultation Service. The participant will be offered referral as appropriate for psychiatric or other evaluation with a clinician and/or for psychiatric assistance with a provider in their home community along with follow up by phone to assure that psychiatric intervention was obtained. For medical problems or conditions that occur outside of the NIH CC, participants will need to seek care and treatment from their primary care physician or a local emergency room.

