5.6.2 Compensation

- There is no compensation for participants that perform the COVID-19 antibody testing only.
- Participants will receive compensation for research activities and interventions, based on research-related inconveniences and time. Participants may receive up to the following amounts, depending on the study arm, assessments performed and optional procedures completed:

	AET+	CON
Study Visit 1 (+ optional measures)	\$ 880 (+\$ 90)	\$ 880 (+\$ 90)
Study Visit 2 (+ optional measures)	\$ 860 (+\$ 40)	\$ 860 (+\$ 40)
Study Visit 3 (+ optional measures)	N/A	\$ 780 (+\$ 40)
30 Exercise Training Visits at \$30/session	\$ 900	\$ 900
10 Education sessions at \$10/session	\$ 100	\$ 100
Four 3-month follow-ups (\$60/follow-up)	\$ 240	\$ 240
MAX TOTAL (+ OPTIONS)	\$ 2980 (+\$ 130)	\$ 3840 (+\$ 170)

- Payment will be processed after completion of the study visits and each 3-month follow-up period
- Should participants be unable to finish the study, they will be paid for parts completed
- No travel reimbursement will be provided
- For NIH staff participants, please refer to NIH HRPP Policy 404

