8.3.6.8 Impact of Events Scale – Revised (IES-R)

A self-report questionnaire that assesses symptoms of post-traumatic stress disorder (PTSD). The IES-R may be repeated to detect changes over time, and has been used to examine changes in post-traumatic stress among survivors of SARS at 1 and 3 months after hospital discharge ([127](#)). This instrument is available in Spanish.

Scores ≥ 24 indicate that PTSD may be a clinical concern. Participants meeting this threshold will undergo a structured interview by a qualified on-site professional and referred for appropriate medical care by their clinical care provider. Other emergent psychiatric evaluation and treatment will be performed under the guidance of the NIMH Psychiatry Consultation Service. Care will be provided until the participant is stable, can continue research participation or until care can be transferred to the participant's own health care providers. For medical problems or conditions that occur outside of the NIH Clinical Center, participants will need to seek care and treatment from their primary care physician or a local emergency room.

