8.3.9 Accelerometer

Participants will be provided with a small, non-invasive, portable wristwatch accelerometer (Actigraph Inc., Pensacola, FL), to be worn continuously (i.e., 24 hours, 7 days a week) on the participants' non-dominant wrist for collection of free-living physical activity and sleep quality during the course of the study. Participants will begin wearing the accelerometer during the baseline study visit and through to the follow-up assessment time-point (i.e., 10-week follow-up visit for AET+ group or 20-week follow-up visit for CON group). In addition, all participants will be mailed the monitors to be worn for approximately 2 weeks, to coincide with repeated 3-month follow-up periods for one year to capture free-living physical activity and sleep quality outcomes over time.

These small activity monitors have been widely used in large epidemiological studies (NHANES, UK BioBank, etc.) as normative population datasets, and in clinical trials to monitor both population patterns and changes in physical activity, function, and sleep outcomes. Accelerometry signals will be extracted, and overall physical activity levels and sleep duration and quality will be examined using established predictive equations and compared to normative datasets. The device is an FDA 510(k) cleared Class II medical device.

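### The BDI-II response to severe depression or suicidal ideation begins with staff staying beside the participant, but four administrations per participant appear to be off-site, and no review time is set for them

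*Combined protocol and SAP*

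**What the plan says.** **Schedule.** Section 8.3.6 has the questionnaires completed whenever a study visit takes place and then adds: "as well as every 3 months for up to 1 year following the completion of the last study visit, unless otherwise specified". They "may be completed digitally and/or by paper format". The secondary objective on patient-reported outcomes in Section 3 lists depression and post-traumatic stress among the outcomes collected 3-monthly for a year. Section 5.6.2 pays both arms for "Four 3-month follow-ups", and the schedule of activities (Section 1.3) marks patient-reported outcomes at each one.

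**BDI-II response (Section 8.3.6.7).** For severe depressive symptoms or suicidal ideation, "the study coordinator or research staff member will remain with the participant and the PI will be notified". Assessment by the PI or RMD medical staff follows, then psychiatric consultation where needed, referral (including to a provider near home) and a telephone check that care was obtained.

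**IES-R response (Section 8.3.6.8).** Participants scoring 24 or more "undergo a structured interview by a qualified on-site professional" and are referred for care.

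**Events away from the NIH.** Both sections close by telling participants to turn to their own physician or a local emergency room for problems arising outside the Clinical Center.

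**Setting of the follow-ups.** Section 8.3 limits study visits at the NIH to visits 1, 2 and 3. Section 8.3.9 states that "all participants will be mailed the monitors to be worn for approximately 2 weeks, to coincide with repeated 3-month follow-up periods".

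**The concern.** The BDI-II rule reads as if a member of staff is in the room when the form is completed. That fits study visits 1 to 3. It does not fit a form completed at home during the follow-up year, which is the longest and least supervised part of the study.

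At stake is participant safety. The trial asks about suicidal ideation, so it will sometimes hold a positive answer. At a study visit the plan says what happens first. During follow-up its first step is not available, and nothing fixes when the answer will be seen. The steps that could still work all depend on someone having read the form.

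**Working it through.** **1. Are the two scales scheduled in follow-up?** Section 8.3.6 sets the default, and an instrument leaves it only where its own section says so. The VAS-CFS (8.3.6.6) is expressly excluded from the 1-year follow-up, and the PGIC (8.3.6.13) from baseline. The BDI-II and IES-R sections contain no exclusion. Section 8.3.6.8 describes the IES-R as something that may be repeated, which is permissive, but Section 3 places post-traumatic stress in the 3-monthly set. Both scales are therefore in follow-up by default.

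**2. Are the follow-ups off-site?** No sentence says so outright, but the inference is strong:
- NIH study visits are limited to 1, 2 and 3 (Section 8.3).
- At the 3-month time points the schedule of activities marks only questionnaires, activity and sleep monitoring, adverse event review and case report forms.
- The activity monitors are mailed (Section 8.3.9).
- Forms can be completed digitally (Section 8.3.6).

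**3. How many administrations are affected?** The plan's count of four follow-ups agrees with the schedule of activities: weeks 30, 43, 56 and 69 in AET+, and weeks 45, 58, 71 and 84 in CON.

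Share in follow-up = follow-ups / (NIH visits + follow-ups), per scale:

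| Arm | NIH visits | Follow-ups | Share in follow-up |
|---|---|---|---|
| AET+ | 2 | 4 | 4/6 = 67% |
| CON | 3 | 4 | 4/7 = 57% |

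With the planned 38 completers per arm, all followed for the full year:
- Follow-up forms per scale: 2 × 38 × 4 = 304.
- NIH-visit forms per scale: 38 × 2 + 38 × 3 = 190.
- Share: 304 / (304 + 190) = 304/494 = 61.5%.

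With 45 per arm (90 randomized), the figures are 2 × 45 × 4 = 360 and 45 × 5 = 225, so 360/585 = 61.5%.

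The first follow-up falls nominally 16 weeks after the last NIH visit in each arm (30 − 14 in AET+, 45 − 29 in CON).

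**4. Which response steps work at a distance?**

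| Step | Off-site |
|---|---|
| BDI-II: staff stay with the participant | Not possible |
| BDI-II: notify the PI | Possible once the form is read |
| BDI-II: assessment by PI or RMD medical staff | Possible once the form is read; Section 8.2.1 allows telehealth |
| BDI-II: referral and telephone check | Possible once the form is read |
| IES-R: structured interview | Unclear; on-site describes the professional, not the participant |

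**5. When is a remote form read?** No section gives a time or names a reviewer. Section 10.8.1 describes automatic checks on data quality, not alerts for clinical triggers. By contrast, remote exercise sessions have written safeguards: location, contact details and the presence of others are confirmed before each session (Sections 2.3.1.15 and 6.1.1.2).

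**The case against.** The strongest reply is that the protocol does not work only face to face. Most of the BDI-II steps need no physical presence, telehealth is allowed as necessary, both sections have a provision for problems arising away from the NIH, and Section 10.8.1 already uses an electronic module for the self-report questionnaires. Much of this stands, and it rules out several stronger readings that a reader might infer:

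- **That the whole response rule fails off-site.** Only the step of staying with the participant fails. The 67% and 57% are shares falling outside that one step.
- **That the IES-R rule needs the participant on site.** Section 8.3.6.8 asks for "undergo a structured interview by a qualified on-site professional". An on-site professional could interview by telehealth, so the wording is ambiguous and not impossible to follow.
- **That a positive answer in follow-up gets no timely action.** The documents show only that timely action is not assured.
- **That paper forms are mailed and opened long afterwards.** Paper is permitted, but only the monitors are said to be mailed.

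The provision for problems outside the NIH does not close the gap. It relies on the participant to seek care and does not tell the study what to do with a positive answer it already holds. The telehealth provision is optional and not tied to these triggers. The electronic module is not said to flag anything, and Section 8.3.6 still allows paper.

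**Conclusion.** The point holds for the BDI-II in a limited form. At four administrations per participant, 4 of 6 in AET+ and 4 of 7 in CON, the first response step cannot be carried out. No review time or reviewer is stated, so timely action on a report of suicidal ideation is not assured. The IES-R wording needs clarifying in the same edit.

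This rests on two readings: that the follow-ups are off-site, which is inferred, and that the default schedule in Section 8.3.6 applies to both scales. The 304 forms per scale is a ceiling for 76 completers, because Section 8.3 expects some questionnaires to be missed. It counts forms, not positive responses, and the documents give no rate of positive responses. The 16-week interval describes the schedule and is not a response time.

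The sample size, power and primary analysis are not affected. The case for change is that the unresolved situation is suicidal ideation and the correction is cheap.

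**What to change.** Reconcile Sections 8.3.6.7 and 8.3.6.8 with the follow-up schedule in Section 8.3.6:

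1. For off-site administrations, collect the BDI-II and IES-R through the electronic self-report module in CiSTAR that Section 10.8.1 already describes.
2. Flag on submission any response meeting a trigger the protocol already states (severe depressive symptoms, suicidal ideation, IES-R of 24 or more), and send the flag to the PI and RMD medical staff already named.
3. Have the investigators state what applies off-site in place of physical presence, and whether the IES-R interview may be held remotely. The clinical response is theirs to decide.

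The cost is protocol wording and one alert rule in an existing system. The downsides are losing the paper option for two scales at follow-up, and some false alerts.
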